	Appendix 1: Supportive Care Guidelines	

Abbreviation	Meaning
AE	Adverse Event
CFR	Code of Federal Regulations
COH	City of Hope
CR	Complete Response
CRA	Clinical Research Associate
CTCAE	Common Terminology Criteria for Adverse Events
DLT	Dose Limiting Toxicity
DSMB	Data Safety Monitoring Board
FDA	Food and Drug Administration
GCP	Good Clinical Practice
IND	Investigational New Drug
IRB	Institutional Review Board
MTD	Maximum Tolerated Dose
NCI	National Cancer Institute
PD	Progressive Disease
PI	Principal Investigator
PMT	Protocol Monitoring Team
PR	Partial Response
SAE	Serious Adverse Event
SD	Stable Disease

1.0 Goals and Objectives (Scientific Aims)

1.1 Primary Objectives

- 1.1.1 To determine the RR associated with pazopanib as 3rd-line therapy in mRCC patients who have failed therapy with a distinct VEGF-TKI

1.2 Secondary Objectives

- 1.2.1 To determine if baseline HGF, E-selectin and IL-6 are associated with PFS
- 1.2.2 To determine if pre-metastatic niche density in regional LNs is associated with PFS
- 1.2.3 To determine an association between E-selectin, IL-6 and pre-metastatic niche density
- 1.2.4 To evaluate the prognostic effect of pre-metastatic niches as an independent factor in time to first relapse
- 1.2.5 To determine if pSTAT3 in tumor tissue is associated with PFS
- 1.2.6 To describe the toxicity associated with pazopanib in this patient population
- 1.2.7 To evaluate PFS and OS
- 1.2.8 To compare, within patient, time to tumor progression of 2nd-line therapy with time to tumor progression on pazopanib as 3rd-line therapy

2.0 Background

2.1 Current Standards: 1st-Line Therapy for mRCC

Today, the oncologist is armed with a multitude of active agents for the therapy of metastatic renal cell carcinoma (mRCC). An enhanced understanding of pathways related to RCC tumorigenesis has led to the development of clinically validated targeted therapies. At present, these agents can be broadly divided into two classes, inhibitors of vascular-endothelial growth factor (VEGF)-mediated signaling and inhibitors of the mammalian target of rapamycin (mTOR). Substantial evidence exists to support use of the former class of agents as 1st-line therapy for mRCC. VEGF-mediated signaling may be abrogated by inhibition of the intracellular tyrosine kinase domain of the VEGF-receptor with agents such as sunitinib, or by neutralization of circulating VEGF with agents such as bevacizumab. In a randomized, phase III trial including 750 previously untreated patients with metastatic clear cell RCC, sunitinib was shown to improve overall survival (OS) as compared to IFN- \square (26.4 mos vs 21.8 mos, P=0.051).⁷ With censoring of patients who crossed over to sunitinib therapy, this difference was even more pronounced (26.4 mos vs 20.0 months, P=0.036). Data for bevacizumab derived from two phase III trials (AVOREN and CALGB 90206) suggests substantial activity as first-line therapy for mRCC in combination with IFN- \square ; however, survival data with bevacizumab fails to surpass the “highwater mark” achieved with sunitinib.⁸⁻¹⁰

Within the past several months, a distinct VEGF-TKI has gained FDA approval for the treatment of mRCC. The novel TKI pazopanib demonstrates strong affinity for VEGFR-2 (inhibiting the moiety at serum concentrations of 17.5 mcg/mL), and was recently examined in a pivotal phase III trial.¹¹ In this study, 400 patients with clear cell mRCC and either no prior therapy or 1 prior cytokine-based therapy were randomized in a 2:1 fashion to receive pazopanib at 800 mg oral daily or placebo. The study met its prior endpoint of improved PFS (9.2 vs 4.2 mos, P<0.0000001), and showed an even more impressive difference in PFS amongst treatment-naïve patients enrolled (11.1 vs 2.8 mos, P<0.0000001). The agent

was well tolerated, with diarrhea, hypertension and hair color change representing the most frequent treatment-related adverse events. Already, the agent has been allotted a category 1 recommendation (along with bevacizumab/IFN and sunitinib) in the National Comprehensive Cancer Network (NCCN) Clinical Practice Guidelines.¹²

2.2 Current Standards: 2nd-Line Therapy for mRCC

Subsequent to failure of a VEGF-TKI, there is a role for therapy with the mTOR inhibitor everolimus. A phase III experience with this agent has been reported, randomizing 416 patients who had previously progressed on VEGFR-tyrosine kinase inhibitor (TKI) therapy to either everolimus or placebo.⁵ Results from a second interim analysis of this trial demonstrate a substantial increase in PFS with everolimus therapy (4.9 mos v 1.9 mos, P<0.001). OS associated with everolimus therapy was 14.8 months; taken together with data from the phase III experience with sunitinib, OS for patients with advanced RCC can now be projected at upwards of 41 mos with initial sunitinib therapy followed by everolimus.

2.3 Beyond 2nd-Line Therapy for mRCC

Trials are currently ongoing to determine the optimal sequencing of therapy in mRCC. As one example, RECORD-3 will compare 1st-line therapy with either sunitinib or everolimus, followed by crossover to the other agent at the time of progression.¹³ Though such efforts will optimize 1st- and 2nd-line therapy, there is currently a need for trials exploring approaches beyond failure of antiangiogenesis and mTOR inhibitors in mRCC. At present, observational studies suggest that oncologists frequently re-challenge patients with a VEGF-TKI after initial failure.¹⁴ Although somewhat counter-intuitive, data from these series suggest that (in the 2nd line setting) patients may have a higher response rate to re-challenge with a VEGF-TKI as compared to an initial challenge with an mTOR inhibitor. A retrospective analysis of patients given consecutive treatment with sorafenib followed by sunitinib demonstrated response rates of up to 17% with sunitinib therapy.¹⁵ Impressively, in a similar analysis of patients receiving a reversed schedule of these agents, one patient treated with sunitinib followed by sorafenib exhibited a complete response.

2.4 Rationale for Pazopanib as 3rd-Line Therapy

Though the approach of re-challenging mRCC patients with VEGF-TKI therapy appears to be reasonably efficacious in retrospective series, clearly this strategy warrants further prospective validation (the ongoing AXIS and SWITCH studies may define the feasibility of this approach).¹⁶⁻¹⁸ Pazopanib has shown activity in the setting of bevacizumab- and cytokine- refractory patients.^{1,2} Furthermore, there may be preclinical rationale to challenge patients with a structurally distinct VEGF-TKI. Molecular aberrations in the receptor tyrosine kinase (RTK) targeted by VEGF-TKIs may confer a relative resistance to specific agents – thus, re-challenging with agents such as sunitinib is presumably less efficacious.^{3,4} Ongoing studies have assessed inhibition of distinct molecular pathways; however, response rates using this approach (i.e., with mTOR inhibitors or perifosine) have been modest at best.^{5,6} 3rd- line therapy represents an area of need in metastatic renal cell carcinoma – herein, we propose use of pazopanib in this setting.

2.5 Cytokine and Angiogenic Factors (CAFs): Potential Predictors of Response?

Responses observed with pazopanib therapy may be augmented by appropriate selection of patients with sensitivity to the agent. Data from a randomized discontinuation trial of pazopanib have recently been reported.¹⁹ In this study, 225 patients with mRCC (both treatment-naïve and refractory) were treated with 12 weeks of pazopanib at the approved dose of 800 mg oral daily. Patients were continued on therapy thereafter if a CR or PR was obtained, and discontinued if PD was observed. Initially, patients with SD

were randomized to either pazopanib or placebo; however, in light of robust clinical activity, this randomization was ultimately halted. On independent review, pazopanib was associated with a clinical benefit rate (CBR; CBR = CR + PR) of 34.7%, and a median OS of 11.9 mos.

Correlative analyses to accompany this study included comprehensive assessment of CAFs obtained at baseline and during therapy.²⁰ Elevated levels of HGF, IL-6 and IL-8 were significantly correlated with less tumor shrinkage in patients treated with pazopanib. Lower IL-6 baseline levels of IL-6 were associated with a profound improvement in PFS (77.7 v 28.6 wks). Notably, other studies have suggested the predictive and prognostic relevance of IL-6 in the setting of distinct therapies.^{21,22} While the data presented herein is encouraging, prospective validation is necessary to determine the true clinical utility of IL-6 as a predictive marker with pazopanib therapy.

2.6 IL-6/STAT3: Role in RCC Tumorigenesis

IL-6 may play a role in RCC tumorigenesis through activation of STAT3-related pathways.²³ Seminal observations by Yu and Figlin indicate that inhibition of STAT3 activation by VEGF-TKIs correlates with their apoptotic effect.²⁴ This may occur through a multitude of mechanisms, including immune modulation. *In vivo* experiments suggest that VEGF-TKI therapy leads to decreased STAT3 activation in tumor-associated myeloid-derived suppressor cells (MDSCs), and further decreases the quantity of tumor MDSCs and tumor T-regulatory cells.

In the current proposal, the role of IL-6 as a predictive marker is examined in the context of 3rd-line therapy with pazopanib. Given that 3rd-line therapy for mRCC represents an area of need and that the majority of patients will have already encountered previous treatment with a VEGF-TKI, use of relevant biomarkers to select appropriate patients is paramount. Correlative studies assessing the role of STAT3 may validate the purported role of IL-6 in RCC tumorigenesis.

2.7 Other Biomarkers of Pazopanib Response Identified in the Randomized Discontinuation Study

Outside of IL-6 level, data from the randomized discontinuation study of pazopanib previously cited provided hypothesis-generating data regarding the prognostic role of E-selectin. Specifically, using a two-factor signature with E-selectin and IL-6, selected groups with significantly different PFS could be identified. Patients with low IL-6 and high E-selectin had superior PFS (median: 100 wks) in comparison to those patients with high IL-6 and low E-selectin (median: 28.3 wks). An intermediate group of patients comprised of patients with high or low levels of both IL-6 and E-selectin had a median PFS of 53.0 wks.

2.8 Unifying E-Selectin and IL-6: The Pre-Metastatic Niche

A “seed-and-soil” hypothesis has been *en vogue* as an explanation for metastatic progression in multiple malignancies.²⁵ Recently, strong preclinical rationale has emerged for this hypothesis, suggesting that bone marrow derived cells (BMDCs) are stimulated to migrate to ‘pre-metastatic’ sites by various inflammatory cytokines, including IL-6.^{26,27} As outlined on the following page, the pre-metastatic niche is cultivated into an area conducive to tumor migration through various molecular mediators which modify the extracellular matrix. Strong evidence implicates the role of E-selectin, VEGFA and LOX, amongst other moieties, in this process.^{28,29}

Given the role of both IL-6 and E-selectin in this model, the currently proposed study offers a prime opportunity to explore whether the pre-metastatic niche can explain their prognostic role. In the setting of mRCC, the niche can be assessed in regional lymph nodes (LN_s) harvested at the time of nephrectomy.

Pre-metastatic niche density (characterized as the number of clusters of VEGFR1⁺VLA-4⁺ cells per x 100 objective field) can be used as a quantitative assessment.

This study will be conducted in compliance with the protocol, Good Clinical Practice (GCP) and the applicable regulatory requirements.

3.0 Patient Eligibility

3.1 Inclusion Criteria

- 3.1.1 Histologically confirmed diagnosis of metastatic clear cell RCC
- 3.1.2 At least one measurable lesion at baseline as per RECIST 1.1 criteria. If skin lesions are reported as target lesions, they must be documented (at baseline and at every physical exam) using color photography and a measuring device (such as a caliper) in clear focus to allow the size of the lesion to be determined from the photograph
- 3.1.3 1 prior VEGF-TKI required
- 3.1.4 1 other prior systemic therapy allowed
- 3.1.5 ECOG PS 0-1
- 3.1.6 Resolution of grade ≥ 2 toxicity from prior therapy
- 3.1.7 Normal hematologic labs and serum chemistries (see table 1, under 3.1.12 for definition of normal)
- 3.1.8 Subjects must provide written informed consent prior to performance of study-specific procedures or assessments, and must be willing to comply with treatment and follow-up. Procedures conducted as part of the subject's routine clinical management (e.g., blood count, imaging study) and obtained prior to signing of informed consent may be utilized for screening or baseline purposes provided these procedures are conducted as specified in the protocol.
- 3.1.9 Age ≥ 18 years or legal age of consent if greater than 18 years
- 3.1.10 A female is eligible to enter and participate in this study if she is of non-child bearing potential (i.e., physiologically incapable of becoming pregnant), including any female who has had (1) a hysterectomy, (2) a bilateral oophorectomy (ovariectomy), (3) a bilateral tubal ligation, or (4) is post-menopausal. Subjects not using hormone replacement therapy (HRT) must have experienced total cessation of menses for ≥ 1 year and be greater than 45 years in age, OR, in questionable cases, have a follicle stimulating hormone (FSH) value >40 mIU/mL and an estradiol value < 40 pg/mL (<140 pmol/L). Subjects using HRT must have experienced total cessation of menses for ≥ 1 year and be greater than 45 years of age OR have had documented evidence of menopause based on FSH and estradiol concentrations prior to initiation of HRT.
- 3.1.11 Patients with childbearing potential, including any female who has had a negative serum pregnancy test within 2 weeks prior to the first dose of study treatment, preferably as close to the first dose as possible, and agrees to use adequate contraception. GSK acceptable contraceptive methods, when used consistently and in accordance with both the product label and the instructions of the physician, are as follows: (1) complete

abstinence from sexual intercourse for 14 days before exposure to investigational product, through the dosing period, and for at least 21 days after the last dose of investigational product, (2) oral contraceptive, either combined or progestogen alone, (3) injectable progestogen, implants of levonorgestrel, estrogenic vaginal ring, percutaneous contraceptive patches, intrauterine device (IUD) or intrauterine system (IUS) with a documented failure rate of less than 1% per year, (4) male partner sterilization (vasectomy with documentation of azoospermia) prior to the female subject's entry into the study, and this male is the sole partner for that subject, (6) double barrier method: condom and an occlusive cap (diaphragm or cervical/vault caps) with a vaginal spermicidal agent (foam/gel/film/cream/suppository) Female subjects who are lactating should discontinue nursing prior to the first dose of study drug and should refrain from nursing throughout the treatment period and for 14 days following the last dose of study drug.

3.1.12 Adequate organ system function as defined in Table 1

Table 1. Definitions for Adequate Organ Function

System	Laboratory Values
Absolute neutrophil count (ANC)	$\geq 1.5 \times 10^9/L$
Hemoglobin	$\geq 9 \text{ g/dL (5.6 mmol/L)}$
Platelets	$\geq 100 \times 10^9/L$
Prothrombin time (PT) or international normalized ratio (INR) ^a	$\leq 1.2 \times \text{ULN}$
Activated partial thromboplastin time (aPTT)	$\leq 1.2 \times \text{ULN}$
Total bilirubin	$\leq 1.5 \times \text{ULN}$
Alanine amino transferase (ALT) and Aspartate aminotransferase (AST) ^b	$\leq 2.5 \times \text{ULN}$
Serum creatinine	$\leq 2.0 \text{ mg/dL (133 } \mu\text{mol/L)}$
Or, if $>2.0 \text{ mg/dL}$: Calculated creatinine clearance (ClCR) by Cockroft-Gault formula	$\geq 30 \text{ mL/min}$
Urine Protein to Creatinine Ratio (UPC; appropriate appendix) ^c	<1

- a. Subjects receiving anticoagulant therapy are eligible if their INR is stable and within the recommended range for the desired level of anticoagulation.
- b. Concomitant elevations in bilirubin and AST/ALT above 1.0 x ULN (upper limit of normal) are not permitted.
- c. If UPC ≥ 1 , then a 24-hour urine protein must be assessed. Subjects must have a 24-hour urine protein value $<1 \text{ g}$ to be eligible.

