14.0 Statistical Considerations

14.1 Study Design

The study is an open label, phase II assessment of pazopanib as 3rd-line therapy for mRCC.

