14.1.1 Primary Endpoints

The primary endpoint is the confirmed response rate (CR+PR), as determined by the RECIST 1.1 criteria. We will employ the two stage MinMax design suggested by Simon.

Prior data indicates that an overall RR of 20% can be obtained with pazopanib therapy. For patients with mRCC eligible for this 3rd line study, a response rate of 20% would represent a significant improvement over current approaches (3rd line therapy with the Akt inhibitor perifosine, for instance, yielded a 7% response rate) and would further indicate that the activity of pazopanib is maintained through multiple prior lines of therapy in selected patients.

Prior studies suggest that a response rate between 5-10% would not be an improvement over current approaches. As a result, we have set a discouraging response rate at 8%, and an encouraging response rate at 23%. Initially, we will accrue 14 patients. If there is at least 1 responder, accrual will continue to 28 patients. If 5 or more responders (~18%) are observed, pazopanib will be declared promising for future studies, assuming toxicity and survival endpoints are also within acceptable limits. This Simon's MinMax two-stage design has a type I error of 10% (probability of declaring an agent with a true 8% response rate as promising), and a power of 80% (probability of *not* declaring an agent promising with a true 23% response rate is 20%). All eligible patients treated will be included in the calculation of response rate. Any patients with an unknown response rate will be included as a non-responder.

This design has 31% chance of stopping at the first stage if true response rate is 8%.

Toxicity will be monitored on an ongoing basis. If the number of unacceptable toxicities exceeds 1 in the first 3, or exceeds 2 in the first 6 or more than 25% thereafter, the study will hold accrual for an amendment regarding treatment modifications or study termination.

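### The primary objective is third-line response after failure of a different VEGF-TKI, but the eligibility criteria do not select that population and every eligible treated patient counts toward the 5-of-28 rule

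*Combined protocol and SAP*

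**What the plan says.** Section 1.1.1, repeated in the synopsis, sets the objective: "To determine the RR associated with pazopanib as 3rd-line therapy in mRCC patients who have failed therapy with a distinct VEGF-TKI". Section 14.1 describes the study as a "phase II assessment of pazopanib as 3rd-line therapy for mRCC". Section 14.1.1 discusses the target rate "For patients with mRCC eligible for this 3rd line study" and says that a 20% rate would indicate that "activity of pazopanib is maintained through multiple prior lines of therapy in selected patients".

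The criteria that select patients are 3.1.3, "1 prior VEGF-TKI required", and 3.1.4, "1 other prior systemic therapy allowed". The synopsis words both identically.

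The analysis set is in 14.1.1: "All eligible patients treated will be included in the calculation of response rate". The rule there is Simon's minimax two-stage design: 14 patients first, continue to 28 if at least 1 responds, and call pazopanib promising at 5 or more responders, provided toxicity and survival are acceptable. The discouraging rate is 8% and the encouraging rate 23%. The 8% comes from the view that "a response rate between 5-10% would not be an improvement over current approaches", with a 7% rate for perifosine, described as third line, as one example.

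**The concern.** The objective defines its population by three attributes: third line, failure of a VEGF-TKI, and a TKI other than pazopanib. The criteria secure none of them. In a single-arm trial the enrolled population is what gives 8% and 23% their meaning, since no concurrent control absorbs a change in case mix. If patients with one prior line enter and count, a positive result could be reported as activity after multiple prior lines when some or all patients had only one. A negative result would be equally hard to attribute to third-line patients. Describing the sample afterwards cannot restore 28 evaluable third-line patients.

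**Working it through.** **1. Objective against criteria**

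| Attribute in the objective | What eligibility does |
|---|---|
| Third line (two prior lines) | One VEGF-TKI is required (3.1.3); one other therapy is only allowed (3.1.4). The two words stand side by side, so allowed cannot mean required. |
| Failure of the VEGF-TKI | No inclusion or exclusion criterion asks for progression or failure. A patient who stopped the TKI for another reason can qualify. |
| A TKI other than pazopanib | No criterion excludes earlier pazopanib. 3.2.2 covers allergy, 3.2.18 a washout before the first dose, and 3.2.21 strong CYP3A4 inhibitors. |

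The first row is a direct contradiction. The other two are omissions. Section 2.1 says pazopanib was approved only months earlier, so prior exposure is probably uncommon.

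**2. Is the gap closed later?** No. Section 14.1.1 takes all eligible treated patients, and no cap, stratum or subset by prior line appears anywhere in section 14. The possible number of one-prior-line patients is 0 to 28.

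**3. Reproducing the stated design**

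Inputs from 14.1.1: first stage 14, stop at 0 responders; total 28, criterion met at 5 or more. With X1 and X2 independent Bin(14, p):

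P(criterion met) = Σ over x ≥ 1 of P(X1 = x) × P(X2 ≥ 5 − x)

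At p = 0.08:

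| x | P(X1 = x) | P(X2 ≥ 5 − x) | Product |
|---|---|---|---|
| 1 | 0.3788 | 0.0214 | 0.0081 |
| 2 | 0.2141 | 0.0958 | 0.0205 |
| 3 | 0.0745 | 0.3100 | 0.0231 |
| 4 | 0.0178 | 0.6888 | 0.0123 |
| ≥ 5 | 0.0035 | 1 | 0.0035 |

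The sum is 0.0675. The same formula at p = 0.23 gives 0.8002. Early stopping at 8% is 0.92^14 = 0.311. So the stated 80% power and 31% stopping probability reproduce. The stated 10% type I error is a ceiling; the attained value is 6.75%. The design arithmetic is sound for a single homogeneous population.

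**4. Illustration of a mixed sample**

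Assumptions, none given by the documents: true third-line response 8%; k of the 28 patients are second line, in random order, so the split over the two stages is hypergeometric; second-line response rate r. The same rule, computed exactly, gives:

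| k | r | P(criterion met) |
|---|---|---|
| 4 | 5% | 5.55% |
| 4 | 8% | 6.75% |
| 4 | 17% | 10.97% |
| 3 | 17% | 9.80% |

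The 5% is the low end of the 5–10% band in 14.1.1. The 17% is the upper retrospective figure in section 2.3 for sunitinib after sorafenib; it is not a pazopanib rate. At r = 8% the answer is 6.75% for every k.

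The rule reaches 10% at a pooled response rate of 0.0899. With r = 17%, that is a second-line share of (0.0899 − 0.08) / (0.17 − 0.08) = 0.110, or 0.110 × 28 ≈ 3.1 patients.

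These are probabilities of meeting the response criterion. The added toxicity and survival condition can only lower the chance of a promising verdict.

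**5. Which population do 8% and 23% describe?** This is unclear. Section 14.1.1 calls the perifosine figure third line, but the title of the abstract cited for it (reference 6) says only that patients progressed after a VEGF receptor inhibitor and gives no line count.

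**6. A related inconsistency.** The within-patient comparison uses second-line therapy as comparator in 1.2.8 and the synopsis objectives, but the previous line in the synopsis statistics; 14.1.2 omits it. The second-line version does not exist for a patient with one prior line.

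**The case against.** The strongest reply is that no error in the decision rule has been shown. The sample size, cut-offs and error rates are correct for whatever population is enrolled, nothing in the documents shows that pazopanib response differs by line, and equal rates give no inflation. In the illustration the excess over the stated 10% is about one percentage point, and it needs 4 patients at a rate taken from another drug. At a second-line rate of 12%, 4 such patients give 8.5%. All of that is right, and the numbers should carry no weight in judging the point. What remains needs no assumed rate: the objective and the conclusion name a population that the criteria do not select.

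A second reply is that the benchmark may already suit the eligible patients, because the reference 6 title is close to 3.1.3. That is possible, but it would support restating the objective rather than leaving it as it is.

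A third is that investigators would enrol third-line patients anyway. Under 5.1 and 13.1.3.1 registration runs through an eligibility checklist, and a patient treated only with a TKI meets the written criteria.

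Finally, section 6.5 replaces patients who receive under 80% of planned first-cycle treatment. How that fits with 14.1.1 is not explained, but it has nothing to do with line of therapy, and 14.1.1 does not remove those patients from the response rate.

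**Conclusion.** The concern holds and should be resolved before accrual. The contradiction on line of therapy is explicit. The missing failure requirement and the missing exclusion of earlier pazopanib are secondary gaps of the same kind. The extent is structural: 0 to 28 of the 28 patients may fall outside the third-line population. The direction and size of any effect on the chance of a positive result are unknown, and no loss of power is claimed. The 5.55% to 10.97% range is illustrative and depends on an assumed 4 second-line patients and assumed rates of 5% to 17%. The conclusion rests only on the wording of 1.1.1, 3.1.3–3.1.4 and 14.1.1.

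**What to change.** Reconcile the objective, eligibility and analysis population in the synopsis and in 1.1.1, 3.1.3–3.1.4, 14.1 and 14.1.1. The sponsor can choose either route.

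- **(a) Align eligibility with the objective.** Require two prior systemic lines, one of them a VEGF-TKI other than pazopanib, and define failure. The 14/28 rule and N = 28 stand. The cost is an eligibility amendment and possibly slower accrual than the 12 months in 14.2.
- **(b) Keep eligibility.** Restate the objective and the 14.1.1 conclusion as response after a prior VEGF-TKI, second or third line; justify 8% and 23% for that population; and report response descriptively by number of prior lines and by earlier pazopanib exposure. N is again unchanged. The cost is rewording, the justification and one table; prior systemic treatments are already recorded at screening (4.1.1.2).

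Separately, use one comparator wording for the within-patient comparison in the synopsis, 1.2.8 and 14.1.2, and limit it to patients who have that prior line.
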